Desirability of outcomes response (DOOR) is an ordinal scale combining current clinical status with SAEs. SAE may be related or unrelated to study product. Any SAE occurring after study product administration through Day 15 (or through Day 29) will be counted:

- 1- Recovered (Ordinal Score Category 1,2,3)
- 2- Improved by at least 1 Ordinal Score from baseline & no SAE
- 3- Improved by at least 1 Ordinal Score Category from baseline & SAE
- 4- No change in Ordinal Score Category from baseline & no SAE
- 5- No change in Ordinal Score Category from baseline & SAE
- 6- Worsened by at least 1 Ordinal Score Category from baseline
- 7- Death (Ordinal Score Category 8)

Oxygenation, Non-invasive ventilation/high flow oxygen, Invasive Mechanical Ventilation/extracorporeal membrane oxygenation (ECMO), hospitalization and mortality will be assessed using results of the Clinical Status 8-point ordinal scale, medical history, and post discharge eCRF questions.

Safety will be assessed by the following:

- Cumulative incidence of serious adverse events (SAEs) through 28 days of follow-up.
- Cumulative incidence of Grade 3 and 4 treatment-emergent AEs.
- Discontinuation or temporary suspension of study product administration (for any reason).
- Changes in white cell count, hemoglobin, platelets, creatinine, total bilirubin, ALT, AST, and INR, d-dimer, C-reactive protein over time. Note D-dimer and CRP are not graded.
- Time to the Composite Endpoint of the first of death, SAE, or Severe AE from the day of first dose of study treatment to the earliest date of any of these events.

Clinical labs will be drawn on Days 1, 3, 5, 8, 11 and on Day 15 and 29 if the subject is able to return to the clinic or is still hospitalized. CRP values from sites using a high-sensitivity assay will be excluded from all CRP summaries and any analyses that use CRP values.

Virologic efficacy is an exploratory endpoint and will be assessed by the following:

- Qualitative and quantitative PCR for SARS-CoV-2 in OP swab on Days 1, 3, 5, 8, 11 (while hospitalized); and Day 15 and 29 (if able to return to clinic or still hospitalized).
- Qualitative and quantitative PCR for SARS-CoV-2 in blood on Days 1, 3, 5, 8, 11 (while hospitalized).

The schedule of study procedures is provided in Section 1.2 of Appendix D of the study protocol.

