For the analysis of mechanical ventilation free survival, subjects will be censored at the time of medication/therapy initiation. For the analysis of the key secondary outcome, if a subject reports use of any of the medications/therapies prior to their Day 15 assessment, then the subject's last clinical status score prior to medication/therapy use will be used as their Day 15 outcome. For the mortality analyses, subjects will be censored at the time of medication/therapy initiation. For the analysis of the proportion of subjects that do not progress to Clinical Status Ordinal Score of 6, 7, or 8 by Day 29, subjects will be censored at the time of medication / therapy initiation. For the recovery analyses, subjects will be censored at the time of medication/therapy initiation. If a subject recovered prior to use of any of the medications/therapies, then the subject will still be counted as a recovery in the sensitivity analysis.

The effect of on-study treatment on select efficacy outcomes will also be explored among subjects who reported use of HMG-CoA reductase inhibitors (statins), angiotensin receptor blockers (ARBs), or angiotensin converting enzyme inhibitors (ACEIs) via subgroup analyses.

Lastly, the effect of treatment on the primary and key secondary efficacy outcomes will be explored via regression modeling controlling for age, duration of symptoms prior to randomization, baseline d-dimer, and baseline CRP values as continuous covariates.

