 - If results are not available for any visit day(s) but are available for visits before or after that visit, the average of the two nearest visits will be imputed for all missing visits between them. If a subject dies or is otherwise lost to follow-up, their last available observation will be carried forward. If baseline is missing, another pre-treatment dose will be used, or the earliest post-treatment dose will be used.

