8.2.1. Sensitivity and Corroborative Analyses of the Primary Endpoint

The primary analysis will be repeated in the As Treated analysis population and in the ITT analysis population. The tabular and graphical summaries described in the previous section will be replicated for this As Treated analysis ([Figure 5](#)) and by baseline ordinal score ([Figure 6](#) and [Figure 7](#)).

Sensitivity analyses will be performed using Cox proportional hazards models to estimate the hazard ratio or progression to mechanical-ventilation or death ([Table 16](#)). A Cox model will be fit with binary indicators for treatment group and actual baseline Clinical Status ordinal score (5 or 6) as well as a treatment * actual baseline Clinical Status score interaction terms. The models will be fit to the mITT analysis population. The treatment group hazard ratios and CIs will be reported for both sets of models and the interaction term p-value will be reported for the interaction models. The tabular summary will also include results from an analysis of time to death or mechanical ventilation controlling for age and duration of symptoms as continuous covariates and baseline d-dimer and CRP values as continuous covariates.

The primary analysis will also be repeated using the other subgroups defined in Section [6.4](#) in place of actual baseline Clinical Status. Each subgroup will be considered separately, and the tabular and graphical summaries described in the previous section will be replicated for each subgroup. A forest plot ([Figure 8](#), [Figure 9](#), [Figure 10](#), [Figure 11](#)) will be generated to display the overall treatment hazard ratio estimate and CI from each of the within-subgroup analyses ([Table 17](#)).

As noted in Section [6.4](#), analyses that take into account concomitant medication will be performed ([Table 18](#) and [Table 19](#)).

In addition, a forest plot will be generated for the “leave one out” sensitivity analyses described in Section [6.7](#) ([Figure 12](#)); estimated proportions and CIs will be provided for each subgroup that leaves a single site out.

Two corroborative summaries will also be generated. A summary of the number and percentage of subjects in each treatment group who:

- recovered (and are alive),
- did not recover and did not require mechanical ventilation or ECMO (and are alive),
- did not recover and required mechanical ventilation or ECMO (and are alive), and
- dead by Day 29.

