8.2.5. Additional Analyses of Time-to-Recovery

The analysis of Time-to-Recovery will be repeated in the mITT population but including only subjects with actual baseline Clinical Status scores in ordinal score 5 or 6 (excluding those with any other baseline score) and in the As-Treated population. The analysis will also be repeated using the Modified Recovery ordinal scale described in Section [4.3](#) ([Table 29](#)).

Sensitivity analyses will be performed using Cox proportional hazards models to estimate the hazard ratio ([Table 29](#)). First, a mITT analysis will be performed in which subjects who die prior to recovering are treated as experiencing a competing risk in the Fine-Gray proportional hazards regression model. Second, a Cox

model will be fit with binary indicators for treatment group and baseline ordinal score (5 or 6) as well as a treatment * baseline ordinal score (as a continuous variable) interaction terms. The models will be fit to the mITT analysis population. The treatment group hazard ratios and CIs will be reported for both sets of models and the interaction term p-value will be reported for the interaction models. The tabular summary will also include results from an analysis of time to recovery controlling for age and duration of symptoms as continuous covariates and baseline d-dimer and CRP values as continuous covariates.

The time-to-recovery analysis will also be repeated using the other subgroups defined in Section 6.4 in place of actual baseline ordinal score. Each subgroup will be considered separately, and the tabular and graphical summaries described in the previous section will be replicated for each subgroup. Forest plots (Figure 18 and Figure 19) will be generated to display the overall treatment hazard ratio estimate and CI from each of the within-subgroup analyses (Table 30).

As noted in Section 6.4, analyses that take into account concomitant medication will be performed (Table 32). An additional sensitivity analysis will evaluate the effect of recoveries that were not sustained as indicated in Section 3.3.2 (Table 31).

A restricted mean survival time analysis will be performed as an exploratory analysis. The restricted mean recovery time estimates will be provided for each treatment group and actual baseline ordinal score stratum as well as the difference in restricted mean recovery time between treatment groups within each of the baseline ordinal score strata (Table 34).

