P-value calculated using a stratified Chi-square test as in Klein 2007

^a[X] additional subjects are included in the 'Any Baseline Ordinal Score' row that were enrolled with an actual baseline ordinal score of 4. [Include as applicable]

Programming note: Subject may be listed in both Mechanical Ventilation by Day 29 and Dying by Day 29 columns if they required ventilation at any point prior to death. If Dying without ventilation, not included in both.

Table 16: Mechanical Ventilation Free Survival by Day 29 by Treatment Group and Actual Baseline Ordinal Score: Sensitivity and Exploratory Analyses – mITT Population, Actual Baseline Ordinal Score 5 or 6

Model	Treatment Group	Actual Baseline Ordinal Score	HR		Interaction P-value ^a
			Estimate	95% CI	
Covariate-Adjusted	Baricitinib + PBO + RDV (N=X)	Baseline Ordinal Score 5 or 6	x.xx	x.xx, x.xx	0.xxx
	PBO + Dexamethasone + RDV (N=X)		x.xx	x.xx, x.xx	
Treatment Arm-Baseline Ordinal Score Interaction	Baricitinib + PBO + RDV (N=X)	5	x.xx	x.xx, x.xx	0.xxx
	PBO + Dexamethasone + RDV (N=X)		x.xx	x.xx, x.xx	
	Baricitinib + PBO + RDV (N=X)	6	x.xx	x.xx, x.xx	
	PBO + Dexamethasone + RDV (N=X)		x.xx	x.xx, x.xx	
	Baricitinib + PBO + RDV (N=X)	Baseline Ordinal Score 5 or 6	x.xx	x.xx, x.xx	
	PBO + Dexamethasone + RDV (N=X)		x.xx	x.xx, x.xx	

HR is the ratio of the hazard of mechanical ventilation or death in each treatment group estimated from the indicated model. The ratio is PBO + Dexamethasone + RDV to Baricitinib + PBO + RDV.

HR for the Baseline Ordinal Score 5 or 6' group is the hazard ratio from the stratified Cox Model.

Covariate adjustment is by age, duration of symptoms prior to randomization, baseline d-dimer, and baseline CRP values as continuous covariates. High-sensitivity CRP values are excluded from this analysis.

Estimates are HR and CIs from interaction Cox models. For the interaction models, HRs are calculated at the level of each individual ordinal score category.

a P-values are from the likelihood ratio test.

Programming Notes:

For the “Treatment Arm-Actual Baseline Ordinal Score Interaction”, the ordinal score covariate will be treated as a categorical variable.

Tables with similar format:

Table 17: Mechanical Ventilation Free Survival by Day 29 by Treatment Group within Subgroups – mITT Population, Actual Baseline Ordinal Score 5 or 6

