Other Anti-Inflammatory Drugs	Baricitinib + PBO + RDV (N=X)	X.XX	X.XX, X.XX	--
	PBO + Dexamethasone + RDV (N=X)			
Covariate-Adjusted Model				
Covariate-Adjusted	Baricitinib + PBO + RDV (N=X)	X.XX	X.XX, X.XX	--
	PBO + Dexamethasone + RDV (N=X)			
Interaction Models				
Treatment-Continuous Actual Baseline Ordinal Score (5 or 6) Interaction	Baricitinib + PBO + RDV (N=X)	X.XX	X.XX, X.XX	--
	PBO + Dexamethasone + RDV (N=X)			

^aAnalysis of key secondary endpoint using those subjects in the mITT Population with actual baseline ordinal score of 5 or 6 with actual baseline ordinal score as a model covariate.

Odds ratios for interaction models are calculated at the level of each actual baseline ordinal score.

Programming Notes:

For the Main Analysis, the p-value will only be reported if the p-value from the primary analysis mechanical ventilation free survival is significant. If the p-value will not be reported, then the columns will be removed.

P-value of treatment comparison will only be displayed for the main analysis. For the interaction models, the p-value for the interaction term will be provided in a footnote reading “The p-value for the treatment by actual baseline ordinal score interaction term was 0.xxx.” or “The p-value for the treatment by continuous baseline ordinal score interaction term was 0.xxx.”.

For the covariate-adjusted model, the model will be run with age, duration of symptoms prior to randomization, baseline d-dimer, and baseline CRP values included as continuous covariates. High sensitivity CRP values are excluded from this analysis (denote this in a footnote).

Table with similar format:

Table 22: Odds Ratio for Better (Lower) Clinical Status Score at Study Visit Day 15 by Treatment Using a Proportional Odds Model, Baricitinib + PBO + RDV Relative to PBO + Dexamethasone + RDV – As Treated Population, Actual Baseline Ordinal Score 5 or 6

Programming Note: P-value of treatment comparison will only be displayed for the main analysis. For the interaction models, the p-value for the interaction term will be provided in a footnote reading “The p-value for the treatment by actual baseline ordinal score interaction term was 0.xxx.” or “The p-value for the treatment by continuous baseline ordinal score interaction term was 0.xxx.”.

Table 23: Proportion of Subjects Not Progressing to Clinical Status Ordinal Score 6, 7, or 8 by Day 29 by Treatment Group, Actual Baseline Ordinal Score 5

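### Excluding high-sensitivity CRP values also removes the subjects at those sites from the supportive covariate-adjusted models, because no rule fills the gap

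*SAP*

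**What the plan says.** Section 4.3 gives the assay rule: "CRP values from sites using a high-sensitivity assay will be excluded from all CRP summaries and any analyses that use CRP values". It is worded by site and reaches models as well as summaries.

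Section 6.4 plans, for the primary and key secondary outcomes, "regression modeling controlling for age, duration of symptoms prior to randomization, baseline d-dimer, and baseline CRP values as continuous covariates". Section 8.2.1 places such a model for time to ventilation or death in Table 16, with "baseline d-dimer and CRP values as continuous covariates". Section 8.2.3 carries the same additional analyses over to progression to score 6, 7 or 8 (Table 24). Section 8.2.5 does likewise for recovery in Table 29: "The tabular summary will also include results from an analysis of time to recovery controlling for age and duration of symptoms as continuous covariates", and the sentence goes on to add d-dimer and CRP.

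The shells repeat the exclusion. The footnote to Table 16 reads "High-sensitivity CRP values are excluded from this analysis"; Tables 24 and 29 carry the same footnote, and a programming note to Table 21 has the equivalent. These are worded by value, not by site.

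The only rule for missing CRP is the laboratory item in Section 6.5. It averages the two nearest visits, carries the last value forward after death or loss to follow-up, and for a missing baseline says: "If baseline is missing, another pre-treatment dose will be used, or the earliest post-treatment dose will be used".

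**The concern.** The SAP states what happens to the CRP values but not what happens to the subjects who are left without one. A subject at a high-sensitivity site may have complete age, symptom duration, d-dimer and outcome data, and still fall out of the adjusted model because of the local laboratory method.

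The adjusted rows are meant to support the main results in the same population: Tables 16, 21 and 29 are titled as mITT with baseline score 5 or 6, and Table 24 as mITT with baseline score 5. If they come from a subset of sites, a difference between the adjusted and unadjusted estimates has two possible sources, the covariates and the change of subjects, and nothing planned would separate them.

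**Working it through.** **Step 1: which models need CRP.** The covariate-adjusted rows of Tables 16, 21, 24 and 29 (Sections 6.4, 8.2.1, 8.2.3 and 8.2.5, and the shells). No alternative adjusted model without CRP is described.

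**Step 2: can the value be refilled?** Every route in the Section 6.5 laboratory rule uses the same subject's own CRP: neighbouring visits, the last value, another pre-treatment value, or the earliest post-treatment value. Under the site wording of Section 4.3, all of these are excluded at a high-sensitivity site. No other imputation, missing-value indicator or assay term is given.

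**Step 3: what the software does.** Section 6.1 names PHREG and LOGISTIC for Cox and proportional odds models. Both omit a record with a missing covariate unless it is filled beforehand. The loss of subjects is therefore an inference from Sections 4.3, 6.1 and 6.5 together, not a sentence in the SAP.

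**Step 4: what does not need CRP.** The primary test (Section 8.1.1) adjusts only for baseline ordinal score. The Day 15 model (8.1.2.1) has treatment and baseline score. Progression (8.1.2.2) follows the primary method. Mortality (8.1.2.3) and recovery (8.1.2.4) use log-rank tests.

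**Step 5: size.** The SAP gives no share of subjects at high-sensitivity sites, so there is no figure for the loss to reproduce. The planned total does reproduce: 1382 / (1 − 0.08) = 1502, stated as about 1500 (Section 5).

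Let f be the assumed share of subjects without usable CRP. Then:

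- subjects kept = 1500 × (1 − f);
- standard error relative to keeping all subjects = 1 / √(1 − f), if events are lost in proportion.

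| f (assumed) | Kept of about 1500 | Relative standard error |
|---|---|---|
| 10% | 1350 | 1.05 |
| 20% | 1200 | 1.12 |
| 30% | 1050 | 1.20 |
| 40% | 900 | 1.29 |

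As a check on the second formula, take the design rates of 0.85 and 0.90 in 1382 subjects, with equal arms assumed. Expected events are 691 × 0.15 + 691 × 0.10 = 172.75, and the standard error of the log hazard ratio is roughly 2 / √172.75 = 0.152. At f = 20%, events are 138.2 and the standard error is 2 / √138.2 = 0.170. The ratio is 1.12, as in the table.

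The middle column does not apply to Table 24, which is limited to baseline score 5. The last column does.

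**The case against.** The strongest reply is that nothing confirmatory depends on this. A reader might infer from the phrase covariate-adjusted primary model that the primary result is at risk. The documents do not support that: no test in the hierarchy uses CRP, Section 8.2 calls these analyses supportive, and Section 6.8 gives them no multiplicity control. This stands, and it limits the weight of the point.

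A reader might also infer bias between arms. Section 4.2.3 stratifies randomisation by site, so removing whole sites leaves the comparison within the remaining sites intact. That stands too.

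Nor is the exclusion concealed. Section 4.3 prespecifies it, the shells footnote or note it, and each has an N per arm. But the notes speak of values, and the shells for these four tables do not say whether N counts the population or the subjects in the fitted model.

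It would be tempting to add that the loss cancels the precision that adjustment buys. That does not carry over simply to Cox and proportional odds models, where adjusting for prognostic covariates need not shrink the standard error of the treatment coefficient. For the same reason, adjusted and unadjusted estimates can differ even in identical subjects; a change of subjects adds a second source of difference.

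Finally, leaving out results from an assay judged not comparable is a defensible measurement decision, and it is not disputed here. Whether every subject at a site is lost rests on the site wording of Section 4.3. At a site using both assays, the value wording in the shells could give a different answer.

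**Conclusion.** The point holds for the supportive adjusted rows only. As written, the assay rule, the required CRP covariate and a refill rule that cannot work at those sites together remove subjects from four models presented as mITT analyses. The consequence is a smaller and different population, and an adjusted-versus-unadjusted contrast that mixes covariate adjustment with a change of subjects. The primary conclusion and the hierarchy are untouched, and no bias between arms follows.

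The size cannot be fixed from the SAP. A standard error larger by 5% to 29% corresponds to an assumed loss of 10% to 40% with events lost in proportion; the true share could be smaller. The conclusion also assumes default handling of missing covariates in the named procedures. It is a cheap improvement, not a flaw in the main analysis.

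**What to change.** Keep the exclusion of high-sensitivity values in both the CRP summaries and the models, but state that subjects are not dropped on that account. In the adjusted models of Tables 16, 21, 24 and 29, where baseline CRP is excluded or missing, set it to the mean of the usable baseline values and add an indicator that CRP was not usable. Assay choice belongs to the site and is unrelated to arm, so filling this baseline covariate keeps the randomised comparison and all the subjects otherwise eligible for each row. Report the number of such subjects by arm under each table. Use one wording, by site or by value, in Section 4.3 and in the shells.

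The cost is a few sentences in the SAP, one derived variable and one footnote; no new data are needed. The downside is that CRP is adjusted for only coarsely in the subjects concerned.

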5. SAMPLE SIZE CONSIDERATIONS

Sample Size for Primary Analysis

The primary hypothesis will be a test of the difference in proportions surviving without requiring invasive mechanical ventilation between the two treatment arms by Day 29. Estimating the expected treatment effect of baricitinib relative to dexamethasone is difficult given the differences between the ACTT-2 and RECOVERY studies as discussed above. In [Table 1](#) the first row of treatment effects is based on estimates from the ACTT-2 and RECOVERY results amongst the cohort that most closely resembles the ACTT-4 target population (those in ordinal 5 and 6). In the second row, the relative findings were changed to assume a gradual improvement in standard of care. This corresponds to a sample size of 1382 subjects. Sample size calculations were based on an exact unconditional score test of proportions using StatXact v11.1.0. Assuming 8% lost to follow-up, the sample size is planned to be approximately 1500 subjects.

The remaining lines demonstrate the power of the proposed sample size. There is good power of this trial for multiple scenarios unless the proportions surviving without invasive mechanical ventilation is much higher than anticipated (thought to be unlikely) or the difference in the proportions is smaller than anticipated (possible, but difficult to anticipate given the data available).

The protocol defined primary analyses were to be based on Kaplan-Meier estimates of the proportion of patients surviving without mechanical ventilation by Day 29 using a large sample normal approximation with Greenwood's variance formula. Accordingly, power for the final analysis is assumed to be equal or slightly higher than the power for the exact score as seen below.

Table 1: Sample Size Estimates and Study Power

Total Sample Size	Proportion Dex Arm Surviving Through Day 29 Without Mechanical Ventilation	Proportion Bari Arm Surviving Through Day 29 Without Mechanical Ventilation	Power (unconditional exact score)	Power (KM + Greenwood)
- Baricitinib from ACTT-2 (OS 5 and 6) - Dexamethasone relative efficacy (only those on oxygen) from RECOVERY applied to ACTT-2 placebo arm	1342	0.814	0.87	80.9% 80.6%
Estimate of the above proportion applied to current outcomes given gradual improvement in care	1382	0.85	0.9	80% 80.5%
Other scenarios showing study power for the sample size of 1382	1382	0.9	0.95	94.5% 94.9%
	1382	0.9	0.925	37.0% 37.5%
	1382	0.85	0.925	99.4% 99.4%
	1382	0.8	0.875	96.6% 96.6%
	1382	0.8	0.85	68.2% 68.9%

Note: two-sided type I error rate 5%; Exact unconditional score test of proportions.

